### 17.4.2 Clinical benefit rate

For initial treatment in each arm, the clinical benefit rate at 24 weeks will be defined as the proportion of patients who completed 6 cycles of treatment without documentation of disease progression. A 90% confidence interval for the CBR will be constructed using the Duffy-Santner approach to take into account the sequential nature of the study design.

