### 17.1 Assessing the impact of adding fulvestrant to alisertib

#### 17.1.1 Primary Endpoint

The primary endpoint is tumor response rate with initial treatment. That is,

- Arm 1: Tumor response rate is defined as 100% times the number of patients who meet the criteria for CR or PR (using RECIST criteria version 1.1) on 2 consecutive evaluations approximately 8 weeks apart during treatment with alisertib monotherapy divided by the number of patients who started alisertib monotherapy.
- Arm 2: Tumor response rate is defined as 100% times the number of patients who meet the criteria for CR or PR (using RECIST criteria version 1.1) on 2 consecutive evaluations approximately 8 weeks apart

during treatment with combination of alisertib and fulvestrant divided by the number of patients who started treatment with the combination of alisertib and fulvestrant.

The study will test the hypothesis that the addition of fulvestrant to alisertib will increase the tumor response rate over that of alisertib alone by at least 20%.

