## 17.2 Sample Size/ Accrual Rate

Melichar et al reported the results of a Phase II clinical trial of alisertib (administered at 50 mg BID for 7 days of a 21 day cycle) monotherapy in women with chemo-resistant metastatic breast cancer. The response rate among the 14 women with triple negative breast cancer was 7.1 % (median PFS: 1.5 months). The response rate among the 26 women with hormone receptor positive disease was 23.1% (median PFS: 7.9 months). Given these results and the expectation that approximately 10% of the patients who will be enrolled onto this trial will have triple negative breast cancer, we anticipate the response rate with alisertib alone will be 20%.

A randomized phase II clinical trial design (proposed by Jung et al) which incorporates a prospective control treatment and a futility stopping rule was chosen to assess whether the tumor response rate with the addition of fulvestrant to alisertib will be greater than that of alisertib alone by at least 20%, when the tumor response rate for alisertib alone is assumed to be 20%. The randomized phase II clinical trial design with a prospective control group proposed by Jung takes into account the interim analysis for futility so that overall design parameters are met.

With a sample size of 45 patients per arm, a one sided alpha=0.15 sequential binomial test of the difference in two independent proportions will have a 85% chance of detecting that the response rate with the addition of fulvestrant to alisertib is at least 20% or greater

than the response rate with alisertib alone, when the true response rate for alisertib alone is 20% or less. The null hypothesis that the difference in tumor responses is less than 20% would be rejected if at least 4 more tumor responses are seen with the combination of fulvestrant and alisertib than with alisertib alone.

It is anticipated that none of the patients who are pre-registered will fail to obtain an ER result from the biopsy of a metastatic lesion. However, some patient may cancel participation prior to registration/randomization or after randomization but prior to the start of assigned treatment and other patients may be found to be ineligible. These patients will be replaced. It is anticipated that an additional 6 patients may be enrolled to account for these situations.

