**Futility stopping rule:** If, after the first 28 patients on each treatment arm have been enrolled and completed at least 6 cycles of treatment, the difference in the number of tumor responses between the treatment arms is one or fewer, enrollment will be halted and the DSMB will be consulted to formulate patient treatment recommendations.

Other Considerations that might lead to early closure: Toxicity, patterns of treatment failure observed in this study and scientific discoveries or changes in standard care will be taken into account in any recommendation to the DSMB to terminate this trial earlier than anticipated.

- 17.2.1 Crossover: Patients who are assigned to alisertib only arm who progress may choose to receive the combination of fulvestrant and alisertib. We anticipate that at least 14 (if there is no signal that combination therapy may be more beneficial) and as many as 22 patients will choose to receive combination therapy. As such, a 95% binomial confidence interval will be constructed for both the tumor response rate and clinical benefit rate during crossover treatment.

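### The 90% interval named for clinical benefit rate needs a stopping boundary on each arm's own count of that endpoint; the trial has none, so the interval cannot be computed as written

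*Combined protocol and SAP*

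**What the plan says.** Section 17.4.2 defines CBR, for initial treatment in each arm, as "the proportion of patients who completed 6 cycles of treatment without documentation of disease progression". It then plans a 90% confidence interval for this rate "using the Duffy-Santner approach to take into account the sequential nature of the study design". It does not say which stopping boundary enters the interval, and the reference list gives no source for the method.

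The only sequential efficacy rule is in section 17.2. It applies "after the first 28 patients on each treatment arm have been enrolled and completed at least 6 cycles of treatment" and halts enrolment if "the difference in the number of tumor responses between the treatment arms is one or fewer". Tumor response is the primary endpoint (17.1.1: "The primary endpoint is tumor response rate with initial treatment"); CBR is listed among the secondary endpoints in 17.1.2. The one formal rule applied to each arm separately is the safety rule in 17.5.2, which counts grade 4 toxicity.

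For patients who cross over, 17.2.1 plans an ordinary 95% binomial interval for response and for CBR.

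**The concern.** A Duffy-Santner interval is a one-sample method for a multistage trial. It orders the possible outcomes by the stage at which the arm stops, and stopping is decided by that arm's own count of successes on the endpoint being estimated. Here the stopping rule differs in two ways: it compares two arms, and it counts tumor responses instead of patients with clinical benefit. There is no arm-level CBR boundary to put into the method.

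An analyst following 17.4.2 would have to make one up, possibly with the data in hand, and two analysts could report different limits from the same counts. At stake are the reproducibility and meaning of the error bars on a secondary efficacy endpoint.

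**Working it through.** **1. Confirm that the stopping rule is between-arm.** Inputs from 17.2: "With a sample size of 45 patients per arm, a one sided alpha=0.15 sequential binomial test of the difference in two independent proportions"; it "will have a 85% chance of detecting" the target difference; response 20% against 40%; interim at 28 per arm. Let D1 be the difference in responses (combination minus alisertib) at 28 per arm and D the difference at 45 per arm. Continue if D1 ≥ 2; reject if D ≥ 4. Then

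P(reject) = Σ over d ≥ 2 of P(D1 = d) × P(D2 ≥ 4 − d),

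where D2 is the difference from the further 45 − 28 = 17 per arm. Exact binomial convolution gives:
- 20%/20%: alpha 0.147, probability of stopping early 0.693;
- 20%/40%: power 0.850, probability of stopping early 0.110.

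These reproduce the stated 0.15 and 85%, so the design's sequential feature is this between-arm rule.

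**2. Can a CBR cut stand in for it?** Assume response 20% and CBR 54% in both arms (54% is the alisertib figure in 3.2.2.1 and 17.4.3), with every responder counted as clinical benefit. The chance of stopping, given the arm's own CBR count at 28, is:

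| CBR count | Alisertib arm | Combination arm |
|---|---|---|
| 10/28 | 0.45 | 0.91 |
| 15/28 | about 0.70 | about 0.70 |
| 20/28 | 0.86 | 0.46 |

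The relation is gradual and runs in opposite directions in the two arms. No cut on an arm's own CBR count reproduces it.

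**3. Do the limits depend on an invented cut?** As an illustration, impose stopping at X1 ≤ c of 28 and use a stage-wise ordering (this is not the exact Duffy-Santner ordering). For 20/45 the lower limit solves P(X1 > c, X ≥ 20) = 0.05, and the upper limit solves P(X1 ≤ c) + P(X1 > c, X ≤ 20) = 0.05.

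| Invented cut | 90% limits for 20/45 |
|---|---|
| none (Clopper-Pearson) | 31.7% to 57.7% |
| ≤10/28 | 32.0% to 58.0% |
| ≤12/28 | 33.4% to 60.7% |
| ≤14/28 | 37.2% to 66.7% |
| ≤15/28 | 40.1% to 69.9% |

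The shift from the plain interval runs from 0.3 points at each end (cut ≤10) to 40.1 − 31.7 = 8.4 and 69.9 − 57.7 = 12.2 points (cut ≤15).

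**4. Does a plain exact interval survive the real rule?** For each arm, let S(x) be the probability that the trial stops with x of 28 benefiting, and C(x) the probability that it continues and ends with x of 45. With true rate p,

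coverage = Σ S(x)·1[p in CP(x, 28)] + Σ C(x)·1[p in CP(x, 45)],

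bias = Σ S(x)·x/28 + Σ C(x)·x/45 − p.

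Exact enumeration, every responder counted as clinical benefit, values given as alisertib / combination:

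| Response | CBR | P(stop) | Coverage | Bias (points) |
|---|---|---|---|---|
| 20% / 20% | 54% / 54% | 0.69 | 91.7% / 92.2% | +0.4 / −0.4 |
| 23% / 23% | 50% / 50% | 0.68 | 92.0% / 91.9% | +0.5 / −0.5 |
| 20% / 40% | 54% / 74% | 0.11 | 92.3% / 93.5% | +0.2 / −0.2 |
| 20% / 40% | 50% / 60% | 0.11 | 92.4% / 90.3% | +0.2 / −0.3 |
| 20% / 20% | 30% / 30% | 0.69 | 90.9% / 92.0% | +0.6 / −0.7 |

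For comparison, at CBR 54% with no stopping rule the same interval covers 91.4% at n = 28 and 92.8% at n = 45. If 20% of responders lack clinical benefit, coverage in the five scenarios is 90.6% to 93.7% and bias is at most 0.5 points. In an extreme corner, where response and CBR coincide at 30% in both arms, bias reaches 0.9 points and coverage is 90.9% / 92.4%.

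**The case against.** **The documents do not describe the method.** That is true: its one-sample, own-boundary nature is general statistical knowledge about a named method. Even without it, 17.4.2 leaves open which boundary is used and how it relates to 17.2, so the gap remains.

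**The planned limits were never shown to be wrong.** This stands. A reader might infer from step 3 that the reported limits would be off by 8 to 12 points. The documents do not support that. The ordering used is illustrative, and the large shift needs a cut at 15/28 (53.6%), about the 54% the protocol cites for alisertib alone. Nothing in the plan suggests such a cut. Reaching 20/45 under it also requires at least 16/28 in stage one followed by at most 4/17. With a cut at 10/28 the shift is 0.3 points.

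**The endpoint is secondary.** This also stands. No test, stopping decision or sample size uses the interval. A reader might infer that the primary comparison or the futility rule is compromised; step 1 shows that both match the stated alpha and power.

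**A plain interval raises its own problem at a futility stop.** Section 17.2 does not say that accrual pauses while the first 28 per arm complete 6 cycles. Dividing by everyone treated at that moment would count recently started patients as failures. The denominator and timing therefore have to be specified.

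**Responders need not have clinical benefit.** Confirmed response (two evaluations about 8 weeks apart, imaging every 2 cycles) can precede progression before the end of cycle 6. The check with 20% of responders lacking benefit covers this and does not change the result.

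**Conclusion.** The point holds as a mismatch between method and design: 17.4.2 names an interval that needs an arm-level CBR boundary, and the trial stops on a between-arm difference in responses. As written, the interval cannot be computed without a boundary that the plan does not contain.

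The size of any resulting error is not established, and the consequence is confined to the error bars of a secondary descriptive endpoint.

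In the scenarios examined, the actual rule barely disturbs an ordinary exact interval: coverage is about 90% to 94% and bias at most about 0.7 points (0.9 in the extreme corner). This assumes exactly 28 per arm at a stop and the stated links between response and benefit. The figures average over stopping and continuing. Given an early stop in the first scenario, the expected CBR is 55.5% (alisertib) and 52.4% (combination) against a true 54%. It would go too far to say that a sequential correction is never needed, since only these scenarios were checked.

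**What to change.** In 17.4.2, replace the Duffy-Santner interval with an exact binomial (Clopper-Pearson) 90% interval for CBR in each arm, consistent with the ordinary binomial interval already planned for crossover in 17.2.1. State the denominator as all patients who started the assigned initial treatment. State the timing as once each of them has completed 6 cycles, progressed or discontinued, so that recently started patients at a futility stop are not counted as failures.

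If a sequential interval is preferred, the plan should specify before analysis how it is derived from the between-arm response rule in 17.2.

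The cost is a few sentences of text. Sample size, data collection and the primary analysis are unchanged; after an early stop, the CBR analysis waits for the last treated patients to reach one of the three end points.

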### 17.4.3 Examination of baseline and 4 week on initial treatment tumor biopsy specimens

Spearman rank correlation coefficient will be used to examine the association between ER $\alpha$  expression and the biomarkers: CD44, CD24, total and phosphorylated expression of AURKA, SMAD5, and SOX2 at baseline. Assuming that 90% of the 90 patients enrolled onto this trial will have sufficient baseline tissue to complete these analyses; there will be 81 patients will data available for these analyses. With a sample size of 81, a two-sided alpha=0.05 test of Spearman rank correlation coefficient will have a 90% chance of rejecting the true correlation is 0 when the true correlation is 35% or more.

A two sample test of the difference in proportions will be used to examine whether weak or no phosphorylated expression of AURKA, SMAD5, and SOX2 after one cycle of alisertib is associated with clinical benefit (CR +PR + SD on treatment for at least 6 months). The clinical response rate in ER+ MBC with single agent alisertib was reported to be 54%. As such we will assume that approximately 50% of the patients enrolled onto each treatment arm will have a documented clinical response. If, in a given treatment arm, 20 patients have a clinical response and 20 patients do not, a two sided alpha=0.05 test of the difference in two independent proportions will have at least an 85% chance of detecting a difference of 45% between the percentage of patients with a no or little expression of the biomarker among those who had clinical benefit and the percentage of patients with a no or little expression of the biomarker among those who did not have clinical benefit when the true percentage of patients with a no or little expression of the biomarker among those who did not have clinical benefit is 10% (or 20% or 25%).

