### 2.3 Correlative Research

- 2.3.1 To assess the changes in Aurora A kinase, SMAD5 and SOX2 expression and phosphorylation in tumor tissue after first cycle of assigned treatment
- 2.3.2 To assess the changes in ER expression and function in tumor tissue after the first cycle of assigned treatment

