### 3.2.2 Evaluation of Aurora A in human breast cancer biospecimens

In translational studies by [REDACTED] (unpublished data), Aurora A kinase, p-SMAD5, p-SOX2 expression was evaluated in a cohort of 100 tissue biospecimens obtained from women with early stage breast cancer treated with optimal locoregional therapy and 5 years of adjuvant endocrine therapy. The “bad outcome” group is defined as patients enduring early breast cancer relapse or death within 5 years of diagnosis, and the “good outcome” group is defined as those with disease-free survival of at least 7 years. Aurora A kinase is measured by immunohistochemistry on a tissue microarray, and the extent and intensity of staining is scored. Tumor samples exhibiting higher levels of Aurora A expression were associated with increased p-SMAD5 and p-SOX2 expression as well as poor clinical outcomes (Figure 3).

These findings are further supported by others. In this study the tumor tissue expression of Aurora A was evaluated in three (3) separate cohorts of women with early stage breast cancer treated without adjuvant therapy (n=766). Their work demonstrated an association of Aurora A with shorter metastases-free survival. The correlation was statistically significant in ER+/HER2- breast cancer, but not in the biologically more aggressive ER-/HER2- or HER2+ molecular subtypes. Further support and validation of our preclinical and translational work is provided by Thrane et al. Thus, patients with ER+ breast cancer and high levels of tumor expression of Aurora A kinase may benefit from targeted treatment with alisertib; in fact, it is feasible that patients with initial ER+ primary disease that is ERlow/- at metastatic relapse or progression may also benefit. These women are known to have particularly inferior clinical outcomes compared with women who retain ER+ expression at relapse.

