- c) Metabolism – Alisertib is metabolized by both oxidation and glucuronidation pathways, and multiple cytochrome P450 (CYP) isozymes (CYP3A4, 2C8, 2C9, 2C19, and 1A2) and uridine diphosphate-glucuronosyltransferase (UGT) isozymes (UGT1A1, 1A3, and 1A8) are involved. Phase 1 oxidative metabolism was identified to be of quantitative importance, with an estimated contribution of CYP3A4 of approximately 60% to overall apparent oral clearance in humans. Therefore, moderate to strong inhibitors of CYP3A4 and clinically significant inducers may alter systemic exposures of alisertib. Given a partial contribution of UGT1A1 to the metabolism of alisertib based on in vitro studies, genotyping for the reduced expression allele UGT1A1 \*28 has been prospectively performed in the clinical program across phase 1 and phase 2 studies. The results of these analyses indicate that pharmacogenetic variation in UGT1A1 is not a meaningful contributor to the variability in the clinical PK of alisertib.
- d) Excretion – Overall mean steady-state terminal half-life following multiple-dose administration of enteric coated tablets in patients with non-hematologic

malignancies was approximately 21 hours. Preliminary results indicate the mean terminal half-life for the oral solution is 22 hours. Negligible urinary excretion of alisertib was observed in humans. The predominant route of elimination for alisertib was fecal, consistent with hepatic metabolism and biliary excretion of alisertib.

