Mandatory tumor tissue specimens for research (see Section 9.0)		X 	X 	X 	X	X 
Research Correlative blood studies (collection for CTCs and cf-DNA)		X	X 	X	X 	X

\* Cycle length is 28 days ±3 days

 The pre-registration biopsy will be utilized for central ER evaluation and correlative studies.

 Performed once up to 4 days prior to the start of Cycle 2. Must be performed prior to initiation of treatment for Cycle 2.

 Performed once up to 14 days after progressive disease is identified. Must be performed prior to initiation of next therapy, which may be the combination of fulvestrant and alisertib for those eligible and electing to crossover, or may be standard therapy for those who elect to come off study or are not eligible for cross-over. If a lung lesion is the only site of disease amenable to a biopsy, then this biopsy will not be mandatory (except for patients with ER <10% or ER negative on the pre-registration biopsy who are desiring and eligible for cross-over).

 Biopsy at PD after crossover is optional, except for patients with a lung lesion as the only site of disease amenable to biopsy in which case the biopsy at PD after crossover is not allowed.

 At the end of Cycle 1, prior to treatment initiation on Day 1 of Cycle 2 (only). May be drawn with clinical labs ≤4 days prior to C2D1.

 At the end of the first cycle of combination therapy, prior to treatment initiation on Day 1 of the second cycle of combination therapy (only).

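### The 17.4.3 test of phospho-markers against clinical benefit uses the post-Cycle 1 level alone, so it cannot tell a marker that was already weak at baseline from one lowered during treatment

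*Combined protocol and SAP*

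**What the plan says.** Section 17.4.3 describes a two-sample test of proportions to examine "whether weak or no phosphorylated expression of AURKA, SMAD5, and SOX2 after one cycle of alisertib is associated with clinical benefit". The outcome is "clinical benefit (CR +PR + SD on treatment for at least 6 months". The power statement takes one arm with 20 patients who benefit and 20 who do not. It says that "a two sided alpha=0.05 test of the difference in two independent proportions" "will have at least an 85% chance of detecting a difference of 45" percentage points, when 10%, 20% or 25% of those without benefit have low expression.

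Objective 2.3.1 is worded differently: "To assess the changes in Aurora A kinase, SMAD5 and SOX2 expression and phosphorylation in tumor tissue after first cycle of assigned treatment".

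The tissue table in 9.2.1 collects the same marker set at pre-registration and after Cycle 1. The Arm 1 calendar (11.1) describes the second biopsy as "Performed once up to 4 days prior to the start of Cycle 2". Section 17.4.3 also uses the baseline phospho-readings, which it expects in 81 of 90 patients, but only to correlate them with ERα.

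Two neighbouring sections use change from baseline:
- 17.4.4 correlates percent change in the tissue markers with maximum tumour shrinkage.
- 17.4.5 plots percent change in circulating tumour cells and in tissue (Aurora A, ER, phospho-SOX2), with symbols for CR, PR, SD and PD.

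Section 3.2.2 reports from early-stage specimens: "Tumor samples exhibiting higher levels of Aurora A expression were associated with increased p-SMAD5 and p-SOX2 expression as well as poor clinical outcomes".

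**The concern.** Because the test sees only the later reading, the weak-or-none group mixes two kinds of patient: those whose marker fell during Cycle 1, and those whose marker was never raised. If the second kind is unevenly spread between patients with and without benefit, the test picks up that imbalance whatever happened to the marker on treatment.

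A significant result would then invite a pharmacodynamic reading that the data cannot carry. Baseline imbalance in the other direction could hide a real link.

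No other planned test relates marker change to clinical benefit. In 17.4.4 the outcome is shrinkage, and a patient with six months of stable disease counts as a benefit while possibly shrinking little. The display in 17.4.5 is visual, uses response category rather than the six-month endpoint, and does not include p-SMAD5.

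**Working it through.** **1. The plan's own power.** Inputs from 17.4.3: n = 20 per group, two-sided alpha 0.05, difference d = 0.45, no-benefit proportion p0 = 0.10, 0.20 or 0.25, p1 = p0 + d. With pooled variance under the null and p̄ = (p0 + p1)/2:

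power = Φ( [d − 1.96·√(2p̄(1−p̄)/n)] / √(p0(1−p0)/n + p1(1−p1)/n) )

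- 0.10 v 0.55: (0.45 − 0.2903)/0.1299 = 1.229, power 89.1%
- 0.20 v 0.65: (0.45 − 0.3064)/0.1392 = 1.032, power 84.9%
- 0.25 v 0.70: (0.45 − 0.3095)/0.1410 = 0.997, power 84.1%

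The stated 85% is reproduced to within a point.

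**2. The same test when the drug does nothing to the marker.** Set each post-Cycle 1 category equal to the baseline category. The test then compares baseline prevalence of weak or none between the two groups. Let a and b be the counts of weak or none in the two groups of 20, and p̂ = (a + b)/40. The rejection probability is the sum over all (a, b) of Bin(a; 20, p0)·Bin(b; 20, p1), counting the pairs where |a − b|/20 exceeds 1.96·√(p̂(1−p̂)/10).

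| Assumed baseline gap | p0 = 10% | p0 = 20% | p0 = 25% |
|---|---|---|---|
| 20 points | 35.7% | 29.1% | 26.9% |
| 30 points | 62.3% | 53.1% | 49.1% |
| 45 points | 90.7% | 84.1% | 82.3% |

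With no gap, rejection is 4–5%. The gap is an assumption, since the documents give no baseline prevalence by benefit status. The 45-point row is the design power again: the test responds to a baseline difference exactly as it does to a treatment-induced one.

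**3. What pairing does.** In 20,000 simulated trials with no drug effect and a 45-point baseline gap, the post-only test rejected in 83–91%. A two-sample comparison of change in weak-or-none status rejected in 0%. With 5–10% random misreading of each biopsy, the figures were 61–81% for post-only and 4–5% for change. Under the same misreading, conversion among patients not weak at baseline rejected in 7–14%.

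**4. Power of the restricted (conversion) version.** Use the formula in step 1 with n = 20(1 − f), where f is the share already weak or none at baseline. The documents do not give f; it is assumed equal in both groups.

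- f = 10%, n = 18: 85%, 81%, 80%
- f = 40%, n = 12: 67%, 62%, 61%
- f = 50%, n = 10: 59%, 53%, 53%

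**5. Time from last dose to biopsy.** The last scheduled alisertib dose of a cycle is on Day 17 (6.1, 6.2). The terminal half-life of the tablets in patients with non-haematologic "malignancies was approximately 21 hours" (8.1.5). From the evening of Day 17:

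- to the morning of Day 25: 180 h / 21 = 8.6 half-lives (0.26% left)
- to the morning of Day 29: 276 h / 21 = 13.1 half-lives (0.01% left)

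With the ±3-day cycle tolerance, Cycle 2 starts between Day 26 and Day 32. The range is then Day 22 (108 h, 5.1 half-lives, 2.8% left) to Day 32 (348 h, 16.6 half-lives). Where Days 15–17 are omitted under 7.3, the interval is a further 7 days, or 8 half-lives.

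**The case against.** The strongest reply is that 17.4.3 claims only an association, that change is the declared subject of 17.4.4, and that 17.4.5 adds a look at change by response. It is right that the plan nowhere calls this a test of drug effect; that reading is a risk of interpretation. It does not remove the gap: neither section tests change against the benefit endpoint.

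Three stronger readings are tempting and are not supported.

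- *Weak expression would go with benefit even without any drug effect.* Section 3.2.2 concerns early-stage patients on adjuvant endocrine therapy, not metastatic patients on alisertib. The same section suggests that patients with high Aurora A may be the ones who gain from alisertib, which would push confounding the other way. The documents support a possible bias of unknown sign.
- *The rejection rates measure the plan's actual error rate.* They follow from an assumed gap and show sensitivity only.
- *The biopsy is too late to see inhibition.* Plasma half-life is not the recovery time of tumour phosphorylation, which the documents do not give. The trial's hypothesis is a change of cell phenotype and restored ER expression, which may outlast the drug.

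Nor should the biopsy be moved to Cycle 2 dosing days. Patients who do not start Cycle 2 would be sampled off drug, and as they cannot complete six cycles they would fall largely in the no-benefit group. Sampling time would then be tied to outcome, and the tissue would be separated from the pre-Cycle 2 blood draw that 17.4.5 compares it with.

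**Conclusion.** The point holds for the missing baseline. As written, the test in 17.4.3 cannot separate pre-existing weak expression from expression lowered during treatment, and no other planned test does so against clinical benefit. The direction and size of any bias are unknown. For assumed baseline gaps of 20 to 30 points, with 20 patients per group and no drug effect, the test would be significant in about 27% to 62% of trials.

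Timing is a limit on interpretation rather than a fault in the schedule. The sample is nominally about 8.6 to 13 plasma half-lives after the last dose, or about 5 to 17 with the cycle window. A null result therefore says nothing firm about inhibition while drug is present.

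This is one correlative analysis; primary and secondary endpoints are untouched. It is still worth correcting before analysis, because the baseline readings are already planned.

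**What to change.** In 17.4.3:

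1. Relate clinical benefit to the post-Cycle 1 category adjusted for baseline category, by a logistic model or, given the small numbers, an exact stratified analysis.
2. Add, as supportive, conversion to weak or none among patients moderate or strong at baseline.
3. Restate power for the expected number of evaluable pairs. State the assumed share already weak at baseline and the assumed correlation between the two readings, since the adjusted test depends on both.
4. Keep the pre-Cycle 2 biopsy window. Report hours since the last alisertib dose, and state that a null result will not be taken as absence of on-drug target inhibition.

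No extra tissue is needed. The costs are these:

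- Patients without a usable baseline reading drop out. Footnote 1 of the table in 9.2.1 allows archival tissue where the biopsy fails, so some pairs will be missing or not contemporaneous.
- The restricted version loses power: about 80–85% if 10% are excluded and 53–59% if 50% are (assumed shares).
- Misread biopsies leave some residual bias in the conversion analysis (7–14% rejection in step 3), which is why it should be supportive. Adjusting for a misread baseline would likewise remove only part of the imbalance.
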